#### Harris Hip Score at 6 weeks, 3 months, 6 months, 1 year and 2 years

Harris hip scores are assessed at the Pre-Op visit and at 6 weeks, 3 months, 6 months, 1 year and 2 years. Results within each visit window will be summarized and changes from baseline will be provided using the Per Protocol Analysis Set. Standard continuous summaries will be supplemented with 95% confidence intervals. The ROM at 6 weeks is considered optional; the score will be missing for Subjects for whom ROM was not performed.

#### HOOS Jr. Score at 6 weeks, 3 months, 6 months, 1 year and 2 years

HOOS Jr. Score are assessed at the Pre-Op visit and at 6 weeks, 3 months, 6 months, 1 year and 2 years. Results within each visit window will be summarized and changes from baseline will be provided using the Per Protocol Analysis Set. Standard continuous summaries will be supplemented with 95% confidence intervals.

#### Forgotten Joint Score (FJS-12)

4 MAR 2022; Version Rev 3 DSJ-2019-02 Confidential Page **30** of **47** 

FJS-12\_are assessed at the 6 week visit and at 3 months, 6 months, 1 year and 2 years. Results within each visit window will be summarized and changes from baseline will be provided using the Per Protocol Analysis Set. Standard continuous summaries will be supplemented with 95% confidence intervals.

#### 11.12.3 Exploratory Endpoint Analysis

Exploratory analyses will include the following:

- Summaries of RSA measured subsidence at 6 Weeks, 3 months, 6 months and 1 year and 2 years will be conducted on the subset of Subjects where RSA data was obtained prior to discharge.
- Correlation of functional and health status outcomes (Harris Hip Score, HOOS Jr, and FJS-12) vs. RSA observations may be explored.
- Summaries of incidence of intraprosthetic dislocation
- Summaries of incidence of intraoperative complications

#### 11.12.4 Comparisons to Historical PINNACLE® Data

All primary, secondary, and exploratory endpoints will be compared to their counterparts in the DSJ\_2018\_02 (PINNACLE® RSA) study for the visits at which those endpoints are assessed using the t-test if the endpoint is continuous or Fisher's exact if the endpoint is categorical. The mean difference (PINNACLE® – PINNACLE® DM), the 2-sided 95% confidence interval for the difference, and the p-value for the test of equality will be presented. There are no formal hypotheses associated with those tests and the p-values and confidence intervals are only presented to facilitate clinical judgment.

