## **3 STUDY SUMMARY**

## 3.1 Protocol Synopsis

Clinical Sponsor	DePuy Synthes Joint Reconstruction
Title	Multi-Center, Non-Controlled, Prospective Radiostereometric Analysis of the PINNACLE ® Dual Mobility Construct
Short Title	PINNACLE® DM RSA Study
Protocol Number	DSJ 2019 02
Indication	Total Hip Arthroplasty (THA)
Study Article Description	PINNACLE ® Acetabular Cup, PINNACLE ® CoCrMo Dual Mobility Metal Liner, a BI-MENTUM ™ ALTRX ® Dual Mobility Polyethylene Liner, a DePuy femoral stem with a polished femoral neck and a DePuy modular, femoral head PINNACLE ® Dual Mobility Metal Liners and Porous-coated PINNACLE ® Acetabular Cups are intended for cementless applications.
Study Design	Multi-Center, Non-randomized, Non-Controlled, Prospective
Study Population	Males and Females aged 21 or older, who are undergoing primary, unilateral THA or revision THA and who may have, in the opinion of the Investigator, a risk of dislocation in the operative joint.
Number of Subjects	N = a minimum of 30 and up to 45
Number of Sites	3 (all Canadian)
Enrollment Timeframe	12 months
Subject Follow-Up	Subjects will be seen at the following intervals: Preoperative, operative, 6 weeks, 3 months, 6 months, 1 year and 2 years postoperatively
Study Objectives	
 
To establish the mean subsidence profile of the PINNACLE® Acetabular Shell and Dual Mobility Metal Liner construct using model-based RSA over the first two years post-implantation
 
To compare study results from this trial to historical PINNACLE® data obtained from DSJ 2018 02.
 

Endpoints	
 
Primary: 
 
RSA measured mean superior cup migration (subsidence: Y translation in mm) at 2 years
 
Secondary: 
 
Comparison of mean superior cup migration at 2 years to historical PINNACLE® data
 
RSA measured subsidence of the PINNACLE® Acetabular Shell at 3 months, 6 months and 1 year and compare to historical PINNACLE® data
 
 
 
 
 

Page 6 of 47

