#### 8.2 Operative (Day 0)

Each Subject will receive a DePuy femoral stem with a polished neck in combination with a DePuy PINNACLE® acetabular cup. All Subjects will receive a PINNACLE® DM metal liner and a BI-MENTUMTM ALTRX® Dual Mobility Polyethylene Liner. Either metal or ceramic heads may be used; however, compatibilities must align with product labeling. Please note since revisions of existing THAs are acceptable to enroll into this study, variations in what is implanted will occur, however Subjects must receive the PINNACLE® DM metal liner and a BI-MENTUMTM ALTRX® Dual Mobility Polyethylene Liner. If the surgeon determines intraoperatively that there exists insufficient bone quality to support the implantation of the construct that Subject will be withdrawn from the study. Subjects that are withdrawn pre-operatively or intra-operatively will be replaced in order to have a minimum of 30 and up to 45 Subjects implanted with the study devices.

Each surgeon shall perform the surgical approach they are most comfortable with and have the greatest expertise.

Implant sizing shall be performed as per the surgeon's discretion for each individual Subject and will not be standardized between sites. Approximately 5-10 tantalum beads will be placed into the

4 MAR 2022; Version Rev 3 DSJ-2019-02 Confidential Page **20** of **47** TV-eFRM-02920 acetabulum. Bead placement will be standardized across study sites to reduce the possibility of unuseable RSA exams resulting from poor bead spacing or bead occlusion.

Any intra-operative adverse events will be captured as well as details of the surgery and implants/components used. The information collected from the 'Operative' time-point will be populated on the appropriate eCRFs as indicated in the Time and Events Table (Section 3.2).

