#### **11.9 General Conventions**

All statistical analysis will be performed using SAS® Version 9.3 or higher, unless otherwise noted. A separate Statistical Analysis Plan (SAP) will provide detail on data derivations and the analyses to be performed for the final study report. It will be approved prior to database lock.

Descriptive statistics for continuous variables will include the number of Subjects with an observation, mean, standard deviation (SD), median, minimum, and maximum. Descriptive statistics for dichotomous/categorical variables will include the count and percentage of Subjects in each category.

Unless specifically stated otherwise, all endpoints will be analyzed by surgical approach and overall, pooling all surgical approaches.

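### Section 11 plans no split by primary or revision THA, and 11.12.4 compares all endpoints with DSJ_2018_02 unadjusted, so a difference in revision share could be read as a construct difference

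*Combined protocol and SAP*

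**What the plan says.** The synopsis (3.1) defines the population as patients "who are undergoing primary, unilateral THA or revision THA and who may have, in the opinion of the Investigator, a risk of dislocation". Sections 6, 7.2 and 8.2 likewise admit both procedures, and none sets a cap or target for revisions. Section 8.2 expects the hardware to differ: "since revisions of existing THAs are acceptable to enroll into this study, variations in what is implanted will occur". Table 1 in 5.5 and Appendix A list revision cups separately from primary cups. The primary endpoint is migration of that shell.

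On analysis, 11.9 gives one breakdown: "Unless specifically stated otherwise, all endpoints will be analyzed by surgical approach and overall, pooling all surgical approaches". Section 8.2 uses the term for operative technique: "Each surgeon shall perform the surgical approach they are most comfortable with and have the greatest expertise". Procedure type is not mentioned anywhere in section 11, nor among the baseline items named in 11.11.

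Section 11.12.4 compares all primary, secondary and exploratory endpoints with DSJ_2018_02 "for the visits at which those endpoints are assessed using the t-test if the endpoint is continuous", or by Fisher's exact test if categorical. The mean difference is reported as PINNACLE minus PINNACLE DM with a 95% interval, and "the p-value for the test of equality will be presented". The same section says that there are no formal hypotheses and that these results serve clinical judgment only. DSJ_2018_02 is described only as using standard PINNACLE constructs (4.2). Its size, eligibility and procedure mix are not given.

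**The concern.** The contrast in 11.12.4 is labelled as one construct against another. Each study's mean is an average over whatever primary and revision hips it enrolled. If the two averages carry different weights, and revision cups migrate differently from primary cups, part of the reported difference is procedure type.

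Comparison with standard PINNACLE is a study objective and a listed secondary endpoint (3.1), and part of the rationale (4.2, 5.1). A reader asked to apply clinical judgment would have no planned table or analysis that separates the two sources.

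**Working it through.** **The plan's own figure.** Section 11.8 gives a margin of 2 × 0.2/√30 = 0.0730 mm, which reproduces. It is the margin for one mean. The synopsis attaches it to the historical comparison, but a difference between two studies has a wider interval.

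**Yardstick for the comparison.** Half-width = t(0.975, n1+n2−2) × SD × √(1/n1 + 1/n2), with SD 0.2 mm (11.8) and 30 subjects in this study. The historical n is not in the documents and is assumed:
- historical n = 20: 0.116 mm
- historical n = 30: 2.002 × 0.2 × √(2/30) = 0.103 mm
- historical n = 45: 0.094 mm

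**Size of the possible shift.** Write each study's mean as its primary-hip mean plus p × d, where p is its revision share and d is the revision-minus-primary gap. With no construct effect, the reported difference is (p historical − p DM) × d. Its absolute size is f × d, where f is the difference in share. Both f and d are assumed, and the shift is zero if either is zero.

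| f | d = 0.1 mm | d = 0.2 mm | d = 0.3 mm |
|---|---|---|---|
| 10% | 0.01 | 0.02 | 0.03 |
| 20% | 0.02 | 0.04 | 0.06 |
| 30% | 0.03 | 0.06 | 0.09 |

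At f = 20%, the shift is 0.02/0.103 = 19% to 0.06/0.103 = 58% of the half-width for 30 v 30.

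**Upper limit implied by the planned SD.** Suppose 0.2 mm is the total SD of the mixed population and the historical set is all primary. Then 0.2² = sw² + p(1−p)d², where sw is the within-procedure SD (assumed). So d cannot exceed √((0.04 − sw²)/(p(1−p))), and the shift cannot exceed p times that.

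| Revision share p | sw = 0.15 mm | sw = 0.18 mm |
|---|---|---|
| 10% | 0.044 | 0.029 |
| 20% | 0.066 | 0.044 |
| 30% | 0.087 | 0.057 |

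Worked line: p = 20%, sw = 0.15 gives √(0.0175/0.16) = 0.331 mm, and 0.2 × 0.331 = 0.066 mm. All six limits lie below 0.103 mm, and some cells of the first table (for example 0.09 mm at f = 30%) lie above them. Under these assumptions the shift matters mainly when the imbalance is large.

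**Precision cost of a primary-only comparison.** With 30 analysed here and 30 historical primaries assumed, the primary-only n is 27, 24 or 21 at 10, 20 or 30% revisions. The half-width goes from 0.103 mm to 0.106, 0.110 or 0.114 mm.

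**The case against.** The case against is substantial, and much of it stands.

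- **No imbalance is shown.** A reader might infer that DSJ_2018_02 enrolled only primary hips and that the comparison is therefore biased. The documents do not support that: the word standard describes the construct, and the historical eligibility is not given. Existence, size and direction of any bias are unknown.
- **Pooling is by omission.** A reader might take 11.9 as an explicit decision to pool primary and revision hips. That sentence concerns surgical approach. Section 11.5 loosens the term somewhat by using it as a gloss on the treatment received. Sections 7 and 8.2 still point to operative technique, so a split by approach would not separate the procedures.
- **The comparison is descriptive.** There are no hypotheses, the intervals are exploratory (11.7), and the sample size was set for the precision of one mean (11.8). This limits what rests on the p-value. It does not remove a shift from the estimate.
- **The gap may be small.** Exclusion 3 removes poor bone quality. Section 8.2 adds that if the surgeon finds during the operation that "there exists insufficient bone quality to support the implantation of the construct that Subject will be withdrawn from the study". Measuring from the 6-week exam (8.7) leaves out earlier migration. All three may reduce d, but none sets it to zero.
- **The separate SAP may deal with it.** Section 11 promises more detail before database lock, and the baseline list in 11.11 is open-ended. Either could add procedure type, but neither commits to it. A baseline table alone would not separate the effect in 11.12.4.

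**Conclusion.** The point holds as a conditional one. With both procedures eligible, no limit on revisions, different shells possible and an unadjusted test, the contrast in 11.12.4 cannot distinguish construct from procedure mix if the mixes differ and revision cups migrate differently. Under the stated assumptions the shift is 0.02 to 0.06 mm at a 20-point difference in share. It cannot exceed about 0.044, 0.066 or 0.087 mm at 10, 20 or 30% revisions if the total SD is 0.2 mm, the within-procedure SD is 0.15 mm and the historical set is all primary. It is therefore mainly an issue at large imbalance.

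Two stronger readings should be resisted. The primary endpoint is not undermined: it is a single-arm mean in the mixed population that the protocol sets out to study, and it does not depend on the historical comparison. Nor would agreement between a pooled and a like-with-like result justify attributing a difference to the construct, because this remains a non-randomized historical comparison. This is a worthwhile, inexpensive improvement to a stated method.

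**What to change.** In section 11 or the separate SAP, before database lock:

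1. In 11.11, tabulate procedure type (primary or revision THA) and shell type (primary or revision cup).
2. In 11.12.4, state the procedure mix of DSJ_2018_02 and keep the pooled t-test. Beside it, for the RSA endpoints, pre-specify a primary-versus-primary comparison, or a model adjusted for procedure type, if the historical data are available by procedure type. Mean, SD and n by procedure type are enough for the former; the model needs subject-level data. Report this study's 2-year subsidence for primary THA as the input, with revisions descriptive only.
3. State that differences between the pooled and like-with-like results will be reported, and that other case-mix differences, such as dislocation risk among primary hips, may remain.

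The cost is wording and a few tables. For this study the information is already collected: treatment history of the index hip (8.1) and "details of the surgery and implants/components used" (8.2). Whether the historical data can be split is not known from the documents. The half-width for the difference rises by about 0.003 to 0.011 mm at 10 to 30% revisions. A revision group of 3 to 9 hips out of 30 is too small for inference. Eligibility and conduct do not change.

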	
 
Other RSA measurements (X and Z translations in mm, X, Y, and Z rotations in degrees, and maximal total point motion in mm) at all time points and compare to historical PINNACLE® data
 
Linear head penetration at 6 weeks, 1 year and 2 years and compare to historical PINNACLE® data
 
Functional and health status as measured with Harris Hip Score, HOOS Jr. and Forgotten Joint Score (FJS-12) and compare to historical PINNACLE® data at baseline and 3 months, 6 months and 1 and 2 years post-operative
 

	
 
Exploratory:
 
Subsidence for subset of Subjects where RSA data was obtained prior to discharge and compare to historical PINNACLE® data
 
Analyses to examine the correlation of functional and
 

	
 
health status outcomes vs. RSA observations may be explored
 
Incidence of intraprosthetic dislocation (IPD)
 

	Incidence of intraoperative complications
	
 
The type and frequency of any serious and non-serious device or procedure-related AEs across all study intervals will be summarized
 

Inclusion Criteria	
 
Individuals requiring THA for a severely painful and/or disabled joint (typically due to non-inflammatory degenerative joint disease); failed previous hip surgery; or dislocation risks.
 

	2. Individuals who are able to speak, read and comprehend the informed patient consent document and willing and able to provide informed patient consent for participation in the study and have authorized the transfer of his/her information to DePuy Synthes
	3. Individuals who are willing and able to return for follow-up as specified by the study protocol
	4. Individuals who are a minimum age of 21 years at the time of consent
	
 
Individuals who are willing and able to complete the Subject Hip Outcomes questionnaires as specified by the study protocol
 

Exclusion Criteria	1. Individuals who have an active local or systemic infection

Page 7 of 47

2.	Individuals who have loss of musculature, neuromuscular compromise or vascular deficiency in the affected limb rendering the procedure unjustified.
3.	Individuals with poor bone quality, such as osteoporosis, where, in the surgeon's opinion, there could be considerable migration of the prosthesis or a significant chance of bone fracture and/or the lack of adequate bone to support the implant(s)
4.	Individuals with Charcot's or Paget's disease

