## **6 SUBJECT DEFINITION**

This study will include male and female Subjects, aged 21 or older, who are undergoing primary, unilateral THA, revision and who may have, in the opinion of the Investigator, a risk of dislocation in the operative joint. Subjects who do not meet all inclusion criteria or who meet any of the exclusion criteria will be excluded from study consideration and participation. Subjects who meet all entry criteria and are properly consented may be excluded from further participation due to study withdrawal, see Section 10 for details.

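### The historical comparison of Harris Hip Score and HOOS Jr. uses an unadjusted t-test on an unstated form of the score, so any difference in pre-operative function enters the reported construct difference

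*Combined protocol and SAP*

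**What the plan says.** Section 11.12.4 of the combined protocol and SAP covers every endpoint: "All primary, secondary, and exploratory endpoints will be compared to their counterparts" in DSJ_2018_02, "using the t-test if the endpoint is continuous or Fisher's exact if the endpoint is categorical". The output is the mean difference (historical construct minus dual mobility construct), and "the 2-sided 95% confidence interval for the difference, and the p-value for the test of equality will be presented". The section adds that "There are no formal hypotheses associated with those tests and the p-values and confidence intervals are only presented to facilitate clinical judgment".

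Harris Hip Score and HOOS Jr. are secondary endpoints (section 11.6.2), so they fall under this rule. Both have a pre-operative value: section 8.1 collects them, and section 11.12.2 states that "Harris hip scores are assessed at the Pre-Op visit and at 6 weeks, 3 months, 6 months, 1 year and 2 years" and that "HOOS Jr. Score are assessed at the Pre-Op visit and at 6 weeks, 3 months, 6 months, 1 year and 2 years". For both, section 11.12.2 provides visit results and also changes from baseline. Section 11.12.4 does not say which of the two enters the t-test.

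No section names a covariate, regression, matching or weighting. The only planned split is by surgical approach (section 11.9). The synopsis (section 3.1) lists the functional scores for comparison with historical "data at baseline and 3 months, 6 months and 1 and 2 years post-operative", and section 5.2 gives the same time points.

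**The concern.** The comparator is an external study of standard PINNACLE constructs (section 4.2), and nothing in the design balances the two groups on pre-operative function. This study takes primary and revision hips and describes its subjects as people who may have, "in the opinion of the Investigator, a risk of dislocation in the operative joint". Inclusion criterion 1 also admits failed previous hip surgery. Such patients could start from a different functional level than those in the historical study.

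Post-operative hip scores usually depend in part on where the patient started. A plain t-test then mixes starting function with whatever the construct did, and the reader asked to exercise clinical judgment cannot separate the two. Because the tested form is not fixed, the sign of the distortion is not fixed either: visit scores and change scores are pushed in opposite directions by the same baseline gap.

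**Working it through.** **The plan's own figure.** The plan gives no SD, correlation, historical mean or precision for the functional scores. Its only statistical figure is the margin of error for mean subsidence in section 11.8: 2 × 0.2/√30 = 0.073 mm. That reproduces, but has no bearing on this point.

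**Set-up.** Let G be the pre-operative mean in DSJ_2018_02 minus that in this study. Suppose the construct has no effect and the post-operative score follows the same straight line on the pre-operative score in both studies, with slope b = r × SD(post)/SD(pre). With equal SDs, b = r. The expected difference (historical minus dual mobility) is then:

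- t-test on visit scores: r × G
- t-test on change scores: r × G − G = −(1 − r) × G
- linear model with the pre-operative score as covariate: r × G − r × G = 0

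**In points.** The values of r and G are assumptions:

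| G (points) | r | Shift, visit scores | Shift, change scores |
|---|---|---|---|
| 4 | 0.3 | 0.3 × 4 = 1.2 | −0.7 × 4 = −2.8 |
| 4 | 0.5 | 0.5 × 4 = 2.0 | −0.5 × 4 = −2.0 |
| 8 | 0.3 | 0.3 × 8 = 2.4 | −0.7 × 8 = −5.6 |
| 8 | 0.5 | 0.5 × 8 = 4.0 | −0.5 × 8 = −4.0 |

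The shift is linear in G, so it is zero if the studies start level.

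**Effect on the p-value.** Assume 30 subjects per study (the size of the historical group is not given), gaps of 0.25 to 0.5 SD and r of 0.3 to 0.7. Rates come from the non-central t distribution and were checked by simulation with 20,000 runs per setting.

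- Visit scores: bias 0.08 to 0.35 SD; a two-sided 5% test rejects in 6% to 27% of cases with no construct effect.
- Change scores: bias 0.08 to 0.35 SD in the other direction; rejection in 7% to 20%.
- Pre-operative score as covariate: bias about 0; rejection about 5%.

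At a gap of 0.5 SD and r = 0.5, either t-test is biased by 0.25 SD and rejects in about 16%.

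**Precision.** With n per group and a gap of d SDs, the adjusted SE divided by the unadjusted SE on visit scores is about √(1 − r²) × √(1 + d²n/(4(n − 1))). The second factor is the cost of the imbalance. For n = 30:

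- d = 0.5: second factor √(1 + 0.25 × 30/116) = 1.032. At r = 0.3, 0.954 × 1.032 = 0.984. At r = 0.5, 0.866 × 1.032 = 0.894. The interval is about 2% to 11% narrower.
- d = 0.8: second factor √(1 + 0.64 × 30/116) = 1.080. At r = 0.3, 0.954 × 1.080 = 1.030. The interval is about 3% wider.

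The case for adjustment is therefore bias, not precision.

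**The case against.** The strongest reply has five parts.

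- **The baseline may already be used.** Changes from baseline are provided, so the t-test may be run on them. It is therefore wrong to infer that section 11.12.4 certainly ignores the pre-operative score. This limits the claim but does not answer it: a change-score test still carries (1 − r) of the gap, with reversed sign.
- **No gap is shown.** The documents say nothing of the case mix or scores in DSJ_2018_02 beyond the use of standard constructs. Inclusion criterion 1 also admits ordinary painful degenerative joints, and section 6 says only that subjects may have a dislocation risk. A reader might infer that the historical patients started from better function. The documents do not support that, and the gaps used above are assumptions.
- **Historical baseline data are inferred.** The time points in sections 3.1 and 5.2 imply that baseline scores exist in DSJ_2018_02. But the same text lists the Forgotten Joint Score at baseline, although section 8.1 does not collect it before surgery and section 11.12.2 starts it at 6 weeks. That wording cannot settle what the historical study holds, nor whether individual records are available. This stands, and the fix has to be conditional on it.
- **One covariate is a partial remedy.** Revision status, indication and dislocation risk can affect outcome at the same pre-operative score. This also stands. It would be wrong to read an adjusted difference as showing that the groups are comparable.
- **The stakes are low.** Sections 11.7 and 11.12.4 disclaim formal hypotheses, a baseline comparison would display any gap, and a separate SAP is still to come (sections 11 and 11.9). The exploratory label answers an error-rate complaint, not a bias complaint. Displaying a gap in one table does not take it out of the difference in another. The pending SAP is the natural place to make the change.

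**Conclusion.** The point holds in a limited form. For Harris Hip Score and HOOS Jr., the plan fixes an unadjusted test against a non-randomised external group and leaves open whether visit scores or changes are tested. If pre-operative function differs between the studies, both versions report part of that gap as a construct difference, in opposite directions. With r of 0.3 to 0.5, equal SDs and gaps of 4 to 8 points, the shift is 1.2 to 4 points on visit scores and 2 to 5.6 points the other way on change scores. All of these inputs are assumptions.

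A reader might go further and infer an inflated error rate for the trial or doubt about its main result. Neither follows. These comparisons are secondary and exploratory, the primary endpoint is RSA subsidence at 2 years, and the sample size rests on that alone. The Forgotten Joint Score and the RSA endpoints have no pre-operative value and are outside this point. What is at issue is a descriptive difference, interval and p-value that can mislead and can be improved cheaply.

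**What to change.** In section 11.12.4 and the separate SAP, for Harris Hip Score and HOOS Jr.:

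1. Specify a linear model of the post-operative score at each visit on study (this study versus DSJ_2018_02) and pre-operative score. Report the adjusted mean difference and its 95% interval beside the unadjusted t-test.
2. State whether the retained t-test uses the visit score or the change from baseline.
3. First confirm that subject-level pre-operative scores from DSJ_2018_02 can be obtained. If only summary statistics exist, this model cannot be fitted; the pre-operative means of both studies should then stand next to each follow-up difference, with a note on how a gap would affect it.
4. State with the result that adjustment addresses starting function only, and that confounding by other factors such as revision status remains.

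The cost is SAP wording and one model per score and visit. Subjects without a pre-operative score drop out of the adjusted estimate, since section 11.15 rules out imputation, so the number contributing should be shown for each analysis.
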